1. PURPOSE OF THE ANALYSES

This statistical analysis plan (SAP) contains detailed information to aid in the implementation of the statistical analyses and reporting of the study data for use in the clinical study report (CSR) for study BBI-4000-CL-303. This SAP is being written with due consideration of the recommendations outlined in the most recent International Conference on Harmonisation (ICH) E9 Guideline, entitled Guidance for Industry: Statistical Principles for Clinical Trials, and the most recent ICH E3 Guideline, entitled Guidance for Industry: Structure and Content of Clinical Study Reports.

This SAP describes the data sets that will be used for analysis, as well as subject characteristics, safety, and clinician-reported and patient-reported perception of disease severity and improvement parameters. The details of the specific statistical methods stated in the protocol will be provided and any changes from the protocol-specified analyses will be documented in the SAP prior to database lock. If additional analyses are required to supplement the planned analyses described in this SAP after the database lock, they may be completed and will be described in the CSR. Table, figure, and listing specifications are provided as an attachment in a separate document. This SAP is based on the latest version of the BBI-4000-CL-303 protocol (Amendment 4) dated 6 May 2019.

Version: 1.0 Page 9 of 51

Brickell Biotech, Inc. Protocol No. BBI-4000-CL-303

2. PROTOCOL SUMMARY

The purpose of this Phase 3 study is to assess the long-term safety, local tolerability, and efficacy of sofpironium bromide gel, 5% and 15% when applied topically in subjects with axillary hyperhidrosis.

2.1 Study Objectives

Primary:

To evaluate the long-term safety and local tolerability of sofpironium bromide gel, 5% and 15% when applied topically in subjects with axillary hyperhidrosis.

Secondary:

- To evaluate the long-term effect of topically applied sofpironium bromide gel, 5% and 15% on Hyperhidrosis Disease Severity Measure-Axillary (HDSM-Ax[©]) in subjects with axillary hyperhidrosis.
- To evaluate the long-term effect of topically applied sofpironium bromide gel, 5% and 15% on patient reported Dermatology Life Quality Index (DLQI) in subjects with axillary hyperhidrosis.

Other:

To evaluate the effect of topically applied sofpironium bromide gel, 5% and 15% on the Hyperhidrosis Quality of Life Index (HidroQoL $^{\odot}$) in subjects with axillary hyperhidrosis. Only the first 100 subjects enrolled will complete this assessment.

2.2 Study Endpoints

2.2.1 Primary Endpoints

Primary endpoints include evaluation of the long-term safety and local tolerability of 5% and 15% sofpironium bromide gel when applied topically in subjects with axillary hyperhidrosis. Assessments will include:

- Adverse events
- Local tolerability assessments
- Vital signs (blood pressure, pulse rate, respiratory rate, and temperature)
- Laboratory tests (hematology, chemistry, and urinalysis) and pregnancy testing in Females of child-bearing potential (FOCBP)

2.2.2 Secondary Endpoints

The following secondary, efficacy endpoints will be analyzed:

• The proportion of subjects achieving ≥1-point improvement in HDSM-Ax-11 (11-item total) from baseline to end of treatment

Version: 1.0 Page 10 of 51

Statistical Analysis Plan

24 February 2020

- The proportion of subjects achieving ≥1.5-point improvement in HDSM-Ax-11 from baseline to end of treatment
- The proportion of subjects achieving ≥2-point improvement in HDSM-Ax-11 from baseline to end of treatment
- Change of HDSM-Ax-11 from baseline to end of treatment as a continuous measure

2.2.3 Other Endpoints

- The proportion of subjects achieving ≥1-point improvement in HDSM-Ax-7 (7item total) from baseline to end of treatment
- The proportion of subjects achieving ≥1.5-point improvement in HDSM-Ax-7 from baseline to end of treatment
- The proportion of subjects achieving ≥2-point improvement in HDSM-Ax-7 from baseline to end of treatment
- Change of HDSM-Ax-7 from baseline to end of treatment as a continuous measure
- The proportion of subjects achieving ≥1-point improvement in the HDSM-Ax-11 score from baseline to each of Visits 2-15 and 17 (Weeks 2-44 and Week 52)
- The proportion of subjects achieving ≥1.5-point improvement in the HDSM-Ax-11 score from baseline to each of Visits 2-15 and 17 (Weeks 2-44 and Week 52)
- The proportion of subjects achieving ≥2-point improvement in the HDSM-Ax-11 score from baseline to each of Visits 2-15 and 17 (Weeks 2-44 and Week 52)
- Change in HDSM-Ax-11 from baseline to each of Visits 2-15 and 17 (Weeks 2-44 and 52) as a continuous measure
- The proportion of subjects achieving ≥1-point improvement in the HDSM-Ax-7 score from baseline to each of Visits 2-15 and 17 (Weeks 2-44 and Week 52)
- The proportion of subjects achieving ≥1.5-point improvement in the HDSM-Ax-7 score from baseline to each of Visits 2-15 and 17 (Weeks 2-44 and Week 52)
- The proportion of subjects achieving ≥2-point improvement in the HDSM-Ax-7 score from baseline to each of Visits 2-15 and 17 (Weeks 2-44 and Week 52)
- Change in HDSM-Ax-7 from baseline to each of Visits 2-15 and 17 (Weeks 2-44 and 52) as a continuous measure
- DLQI from baseline to each of Visits 5, 10, and 16 (Weeks 2, 6, 24, and 48)
- Patient Global Impression of Severity (PGI-S) summarized as frequency counts and percentages for each category (none, mild, moderate, severe, very severe) at each assessment, change from baseline as a 5x5 table with frequency counts and percentages at each post-baseline assessment
- Patient Global Impression of Change (PGI-C) summarized as frequency counts and percentages for each category (very much better, moderately better, a little

Version: 1.0 Page 11 of 51 better, no change, a little worse, moderately worse, very much worse) at Visits 10 and 16 (Weeks 24 and 48)

Exploratory Efficacy Endpoint

HidroQoL from baseline to each of Visits 3 and 5 (Weeks 2 and 6); only the first 100 subjects enrolled in the study were to be eligible complete this assessment.

2.3 Overall Study Design and Plan

This is a multicenter, randomized, open-label, Phase 3 long-term safety study of topically applied sofpironium bromide gel, 5% and 15% in subjects with axillary hyperhidrosis.

A maximum of 300 subjects, at approximately 30 clinical sites, will be enrolled to obtain approximately 150 subjects that have completed 12 months of dosing and clinical assessments.

Subjects will be randomized 1:2 to receive either sofpironium bromide gel, 5% or 15% (100 subjects dosed with 5% gel and 200 subjects dosed with 15% gel). Subjects will apply the investigational product once daily at bedtime, to their axillae for 48 weeks.

Vital signs and adverse events will be collected at each visit. Local tolerability assessments will be collected at each post-Screening visit. Blood and urine samples will be collected and analyzed at Screening and then Week 6 (Visit 5), Week 24 (Visit 10), and Week 48 (Visit 16) for routine hematology, chemistry, and urinalysis parameters. Additionally, a urine pregnancy test for females of child-bearing potential will be collected and analyzed at each visit except at Week 2 (Visit 3), Week 6 (Visit 5), and Week 52 (Visit 17). Patient-reported outcomes HDSM-Ax, PGI-S, PGI-C, and DLQI will be recorded during the study at predefined time points. HidroQoL will be recorded at baseline, Week 2, and Week 6; only the first 100 subjects eligible and enrolled in the study will complete this assessment.

A total of 17 scheduled visits will take place over approximately 52 weeks.

2.4 Study Population

Subjects aged ≥ 9 years with a diagnosis of axillary hyperhidrosis.

2.5 Treatment Regimens

Either sofpironium bromide gel, 5% or 15%, will be topically applied to both axillae once daily at bedtime for 48 weeks.

2.6 Sample Size Determination

A maximum of 300 subjects, at approximately 30 clinical sites, will be randomized to receive either 5% or 15% sofpironium bromide gel in a 1:2 ratio to obtain approximately 150 subjects (50 subjects dosed for 48 weeks with 5% gel and 100 subjects dosed for 48

Version: 1.0 Page 12 of 51

Statistical Analysis Plan 24 February 2020

weeks with 15% gel) who have completed 12 months of dosing and clinical assessments. No formal sample size calculations were performed.

Version: 1.0 Page 13 of 51

3. GENERAL ANALYSIS AND REPORTING CONVENTIONS

3.1 Reporting Conventions

The following is a list of general analysis and reporting conventions to be applied to this study, unless otherwise specified.

All data displays (tables, listings, and figures) will have a header showing the sponsor company name, protocol number, page number, and display status (i.e. "DRAFT" or "FINAL"), as well as a footer indicating path, file name, and run date/time. Summary tables and data listings will be summarized by treatment. All data collected per-protocol and all derived variables will be listed.

Categorical variables will be summarized using counts (n) and percentages (%) and will be presented in the form "n (xx.x)." If a count is 0, 0% will be shown for the percentage. If a percentage is 100%, 100% will be shown with no decimal place. To ensure completeness, summaries for categorical variables will include all categories, even if no subjects had a response in a particular category. Unless otherwise specified, the denominator for each percentage will be based on the number of subjects with available data in the population being summarized. If missing values are present, counts will be shown but will not be included in percentage calculations.

Continuous variables will be summarized using mean, standard deviation (SD), minimum, maximum, median, and number of subjects. The mean and median will be reported to an additional level of precision than the original observation in its rawest form (i.e. on the Case report form (CRF)), and the SD and other measures of variability (e.g. standard error (SE)) will be reported to two additional levels of precision than the original observations. The minimum and maximum will be the same precision as the original data. In general, any calculated values, such as those due to unit conversion, will be rounded to the same number of decimal places as the original data.

No tests of hypothesis of treatment group differences are planned; however, should they be performed as part of exploratory and ad hoc analyses, the associated p-value will be reported. All p-values will be rounded to 4 decimal places. P-values less than 0.0001 will be presented as "<0.0001"; p-values greater than 0.9999 will be displayed as ">0.9999". Any p-values generated will be considered descriptive in nature; there will be no adjustments for multiple comparisons.

Summary tables and data listings:

• No preliminary rounding will be performed; rounding will only occur after analysis.

Version: 1.0 Page 14 of 51

- Data from subjects excluded from an analysis population will be presented in the data listings but will not be included in the calculation of summary statistics, where applicable.
- Data from each subject will be separated by a blank line. Within a data listing, if a descriptive item appears line after line (e.g., repetition of a subject number, date, visit, etc.), only the first occurrence will be displayed (e.g., in Listing of Vital Signs, subject number, date and visit will only be displayed on first row when presenting all parameters collected at same visit). Repetition of actual results or outcomes (e.g., Adverse Events (AEs), lab results, vital sign values, etc.) will not be collapsed.
- Data listings will be sorted by site, subject, treatment, and week and/or time of assessment, unless otherwise noted.
- When change from baseline is calculated, baseline is the last observation obtained prior to dosing of the study drug.

Mock tables and data listings will be provided as attachments to this analysis plan. Minor changes to the mocks after formal SAP approval will not necessitate re-approval unless changes to the text of the SAP are required.

All statistical deliverables will be produced, validated, and reviewed for accuracy/consistency in accordance with Rho, Inc. standard operating procedures and the processes described in the statistical validation plan.

SAS® (SAS Institute, Cary, North Carolina) statistical software, version 9.4 or later, will be used for all analyses. Adverse Events and Medical History will be coded using the most recent version of the Medical Dictionary for Regulatory Activities (MedDRA). Concomitant medications will be coded using the latest version of the World Health Organization (WHO) Drug and Anatomic Therapeutic Chemical (ATC) classification and preferred term.

3.2 Standard Calculations

Unless otherwise noted, baseline is defined as the last observed data value prior to the receiving the first application of treatment for treated subjects, and the last observed data value prior to the randomization date for randomized subjects who were not treated. The baseline derivation can include unscheduled visits.

Study day will be determined as:

• The assessment/event date minus the date of first dose of gel, if the assessment/event date is prior to the date of first dose of gel; and

Version: 1.0 Page 15 of 51

• The assessment/event date minus the date of first dose of gel + 1, if the assessment/event date is on or after the date of first dose of gel.

Note that if the subject is randomized but not treated then the randomization date will be substituted for first dose date of gel.

Change from baseline will be calculated as the post-baseline data value minus the baseline value. Percent change from baseline will be calculated as the change from baseline divided by the baseline value, multiplied by 100.

At any particular time point, for ranked transformation of any data item of interest, all observed data will be ranked together without regard to treatment assignment, from smallest to highest value. The smallest observation will be assigned the rank of 1, the second smallest the rank of 2, and so on. Average ranks will be used for tied observations.

Unless otherwise noted, values reported as greater than or less than some quantifiable limit (e.g., "< 2.0") will be summarized with the symbol suppressed in summary tables and figures, which will use the numeric equivalent.

Partial or missing dates used in calculations of duration may be imputed with logic similar to that of Adverse Events (Section 9.1.1).

Version: 1.0 Page 16 of 51

4. ANALYSIS POPULATIONS

Identification of the subjects to be included in each analysis population will be determined and finalized prior to database lock. Subjects will be classified into the Safety, Intent-to-Treat (ITT), Per Protocol (PP), and HidroQoL (HQL) populations according to the following definitions:

Safety Population

The Safety Population will include all subjects randomized in the study who received study drug at least once. Subjects will be included in the treatment group based on the majority of actual treatment they received (even if not the treatment group to which they were randomized).

ITT Population

The ITT Population will include all subjects who were randomized. Subjects will be included in the treatment group to which they were randomized, regardless of the treatment received.

PP Population

The PP Population will be a subset of the ITT Population and will include subjects who meet the following criteria:

- Meets the inclusion/exclusion criteria
- Has not taken or applied any interfering concomitant medications.
- Completed the following visits:
 - o Visit 1 (Screening) and the required HDSM-Ax data collection
 - o Visit 2 (Baseline) and the required HDSM-Ax data collection
 - o Visit 4 (Week 4), and the required HDSM-Ax data collection
 - o Visit 7 (Week 12), and the required HDSM-Ax data collection
 - o Visit 10 (Week 24), and the required HDSM-Ax data collection
 - o Visit 16 (Week 48), and the required HDSM-Ax data collection
 - o Visit 17 (Week 52), and the required HDSM-Ax data collection
- Treatment received per randomization assignment

HOL Population

The HQL Population will be used for HidroQol analyses. Subjects with "Yes" noted for the question "Subject flagged for the Baseline-Visit 5 HidroQol Protocol" on the Subject CRF page are included. The first 100 subjects \geq 17 years of age enrolled were eligible for this population.

Version: 1.0 Page 17 of 51

5. STUDY SUBJECTS

5.1 Disposition of Subjects

Subject disposition will be summarized for all randomized subjects by treatment group. Summaries will include the number and percentage of subjects in each analysis population, reason for exclusion from the PP population, completing treatment, completing the study, and discontinuing the study early by the primary reason for discontinuation. Analysis populations are defined in Section 4. Treatment completers are subjects with "Yes" noted for the question "Did the subject complete treatment?" on the Study Disposition CRF page. Study completers are subjects with "Normal Study Completion" noted for the question "Subject's Status or Primary Reason for Early Termination" on the Study Disposition CRF page. Study discontinuers are subjects with any response to "Subject's Status or Primary Reason for Early Termination" other than "Normal Study Completion" on the Study Disposition CRF page.

All subject disposition data will be listed for all randomized subjects.

5.2 Protocol Deviations

Major protocol violations will be summarized by treatment group for the Safety Population. Major protocol violations may include, but will not be limited to the following:

- Violation of eligibility criteria;
- Randomization error;
- Non-compliance with study drug dosing;
- On-study administration of a prohibited medication;
- Unauthorized changes to protocol procedure that could potentially affect subject safety or are a flagrant deviation of protocol defined procedures.

All major protocol violations will be determined and appropriately categorized by the sponsor prior to database lock. The number and percentage of subjects with any major protocol violations as well as the number and percentage of subjects with violations within each category will be presented. A by-subject listing will be provided for all protocol violations, major or minor, for the Safety Population.

Version: 1.0 Page 18 of 51

6. DEMOGRAPHIC AND OTHER BASELINE CHARACTERISTICS

Demographic variables including age, sex, ethnicity, race, and predominant race, will be summarized by treatment group for the Safety, ITT, and PP Populations.

Age in years will be summarized using descriptive statistics. Age will also be categorized into 9-12, 13-16, and \geq 17 years of age. Age groups, sex, ethnicity, race, and predominant race will be summarized with the number and percentage of subjects in each parameter category. If more than one race is reported, subjects will be counted in each relevant category.

Baseline characteristics include medical history, height, weight, time since onset of axillary hyperhidrosis symptoms, and body mass index (BMI). Medical history will be summarized for the Safety Population. Other baseline characteristics will be summarized for the Safety, ITT, and PP Populations by treatment group.

Height, weight, BMI, and time since onset of axillary hyperhidrosis symptoms at baseline will be summarized using descriptive statistics. BMI will be calculated as: weight (kg) / (height (cm) / 100)². If height is entered in inches, height is converted to cm by Height (cm) = 2.54 *Height (inches). If weight is entered in lbs, weight is converted to kg by Weight (kg) = 1/(2.2046)*Weight (lbs). Time since onset of axillary hyperhidrosis symptoms will be reported in months and calculated by dividing the duration in days by (365.25 / 12). Duration in days will be calculated as (date of informed consent – start date of axillary hyperhidrosis symptoms + 1).

Medical history events will be coded to system organ class using the most current version of MedDRA. Frequency counts and percentages will be used to summarize subjects reporting abnormal medical history by system organ class. Subjects reporting more than one event for a given system organ class will be counted only once for that system organ class.

All demography, baseline characteristics, and medical history data collected will be presented in listings.

Version: 1.0 Page 19 of 51

Brickell Biotech, Inc. Protocol No. BBI-4000-CL-303

7. MEASUREMENTS OF TREATMENT COMPLIANCE

Study drug compliance will be calculated as the percentage of study drug taken for each subject. Percentage of study drug taken will be calculated by taking into account whether a subject took all doses of study drug as instructed, including protocol indicated dosing modifications collected on the Dosing CRF page. For each dosing entry, percentage of study drug taken will be determined as the total number of doses received divided by the number of expected doses, multiplied by 100.

Expected doses for the study will be calculated as the sum of the expected dose per dosing period (i.e. a 28-day treatment period). The expected dose per dosing period will be calculated as the end date of the period minus the start date of the period, plus one, times a multiplier as shown in the table below. The prescribed frequency for dosing and the multiplier are based on dose reductions allowed per protocol Section 8.1.4.

Table 1. Prescribed Frequencies, compliance dosing multiplier, and reasoning

Prescribed Frequency for Dosing Period	Dosing Multiplier	Reasoning
Daily	2	Drug applied once daily per axilla (2)
PI Withheld	0	No dose administered
Every Other Day	1	Drug applied every other day (0.5), once per axilla (2)
Divided Daily	1	Half (0.5) of drug applied, once daily per axilla (2)
Divided Every Other Day	0.5	Half (0.5) of drug applied, once every other day (0.5), per axilla (2)

The total number of doses received will be calculated as the sum of the number of doses received during the dosing period. The number of doses received during the dosing period will be calculated as the expected dose for the period minus the number of missed doses recorded on the Dosing CRF page for that period.

Percentage of study drug taken over the course of the study will be calculated at the subject-level (i.e. across all dosing entries) and will be summarized by treatment arm using descriptive statistics based on the Safety Population.

Version: 1.0 Page 20 of 51

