5 INVESTIGATIONAL PRODUCT (IP)

Sofpironium bromide gel is an anhydrous gel formulation containing the drug substance in a gel base comprising hydroxylpropyl cellulose National Formulary (NF), hexylene glycol NF, isopropyl myristate NF, citric acid anhydrous United States Pharmacopeia (USP), and alcohol dehydrated USP. Sofpironium bromide gel is a clear to slightly translucent colorless gel and is packaged in a white colored, metered pump container. One pump container is packaged in a carton with 2 applicators. The total gel volume in each pump container is ~50 mL (~43 g). The gross weight of each full container at baseline is approximately 78 to 84 grams.

Based on one full pump actuation delivering ~0.67 mL of the gel formulation, a total of approximately 38 mL of gel is required for 4 weeks (28 days) of daily dosing to the axillae. Therefore, each pump container is sufficient for \geq 28 days of dosing per protocol instructions. A new container will be dispensed to each subject at Baseline and then Weeks 4, 8, 12, 16, 20, 24, 28, 32, 36, 40, and 44.

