5.2 Instructions for Use and Administration of Investigational Product

Investigational product kit cartons will be provided to each site and will include one individual plastic pump container per each carton. Each carton will also contain 2 applicators. An investigational plastic pump container will contain sufficient drug product for a 28-day treatment period.

Each carton will have a unique identifier number printed on the label and the pump container label will display the same unique identifier number.

Each subject will be randomized via an Interactive Response Technology (IRT) system to receive either sofpironium bromide gel, 5% or 15% to topically apply, once daily at bedtime, to each axilla using the supplied applicators for 48 consecutive weeks. Instructions on the use of the IRT system will be provided in a separate manual.

Subjects will be instructed to apply the investigational gel product to each axilla using all the gel expressed from ONE FULL ACTUATION of the pump per each axillary dose application. Each full actuation of the pump corresponds to approximately 0.551 grams for the 5% and 0.576 grams for the 15% investigational product.

The subject will apply all doses of investigational product at night, prior to going to bed using the supplied applicators. Subjects will apply their first dose of gel prior to bedtime on the night of their Baseline Visit. The subject will be instructed to continue applying the investigational product each night with the last application to occur the night before attending the end of-treatment evaluation (i.e., Week 48, Visit 16). Subjects should wash the applicator each night after dosing. Two applicators are provided in each kit to compensate for loss or damage during handling; it is not necessary to use all the applicators over the specified dosing interval.

To ensure accurate dosing, the study staff will be instructed to first prime and then weigh each pump container before dispensing to the subject. Priming is accomplished by fully pressing the pump for five (5) sequential actuations; the dispensed gel from these 5 priming actuations is considered waste and should be discarded.

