9.3 Extent of Exposure

Extent of exposure to study treatment will be summarized for the Safety Population by treatment group. The duration of exposure will be presented in days and summarized using descriptive statistics. Drug (pump) dispensation will be provided in a listing, to include total drug delivered per subject. Each pump will be primed, then weighed, prior to dispensing pumps to subjects. Each pump will be weighed upon return. Total drug delivered will be calculated as the total weight of all pumps dispensed minus the total weight of all returned pumps.

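### The compliance percentage in SAP section 7 cannot exceed 100%, and the pump-weight dose that could show over-use is assigned to a listing and miscounts unreturned pumps

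*SAP*

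**What the plan says.** SAP section 7 gives one compliance statistic: "percentage of study drug taken will be determined as the total number of doses received divided by the number of expected doses". Expected doses are the days in the period times a multiplier, which is 2 for daily dosing (one application per axilla). For the numerator, "The number of doses received during the dosing period will be calculated as the expected dose for the period minus the number of missed doses" on the Dosing CRF page. The subject-level percentage is summarised by arm in the Safety Population.

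The protocol also has a measured dose. Section 5.2 states: "To ensure accurate dosing, the study staff will be instructed to first prime and then weigh each pump container before dispensing to the subject". Each of the 12 containers is weighed again on return. The same section gives a conversion factor: "Each full actuation of the pump corresponds to approximately 0.551 grams for the 5% and 0.576 grams for the 15% investigational product".

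SAP section 9.3 derives total drug delivered as the weight of all dispensed pumps minus the weight of all returned pumps. On reporting it says: "Drug (pump) dispensation will be provided in a listing, to include total drug delivered per subject". The only exposure quantity that section 9.3 says will be summarised is duration in days.

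**The concern.** The numerator starts from the expected dose and can only go down. It treats every application not recorded as missed as exactly one full actuation. More gel than instructed leaves the percentage unchanged, and so does less gel per stroke.

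This matters because the primary objective is long-term safety, and the gel is applied at home, open-label, for 48 weeks. Protocol section 1 describes treatment-emergent events as dose-related and systemic exposure as roughly dose-proportional between 5% and 15%. A reader comparing adverse events between the arms needs to know how much gel each arm used. The planned compliance summary cannot show use above the instructed amount. The variable that could is not summarised by arm in the SAP text, and its formula goes wrong when a pump does not come back.

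**Working it through.** **Reproducing the plan's figure.** Protocol section 5 says about 38 mL is needed for 28 days at about 0.67 mL per actuation. 28 days × 2 axillae × 0.67 mL = 37.52 mL, which agrees.

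**The cap.** Compliance = 100 × (E − M)/E, where E is expected doses and M is recorded missed doses, M ≥ 0. For a 28-day daily period E = 28 × 2 = 56.

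- M = 0 gives 100%; M = 1 gives 98.2%; M = 5 gives 91.1%.
- 20% over-use with nothing missed is 1.2 × 56 × 0.551 = 37.0 g (5%) or 1.2 × 56 × 0.576 = 38.7 g (15%). Weight gives 120%; section 7 gives 100%.
- Three-quarter strokes with nothing recorded as missed give 75% by weight and 100% by section 7.
- If every-other-day dosing is prescribed (multiplier 1, E = 28) and the gel is applied daily, 56 actuations are used against 28 expected. That is 200%; section 7 gives at most 100%.

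**Room for over-use in one pump.** Inputs are from protocol sections 5 and 5.2: fill about 43 g or 50 mL, five priming strokes discarded before the dispensing weight, and the stated grams per actuation. Section 7.1 allows 28 ± 5 days between Visits 7 to 16, so up to 33 days (66 actuations).

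| | 5% gel | 15% gel |
|---|---|---|
| Left after priming: 43 − 5 × g | 40.245 g | 40.120 g |
| Expected, 28 days: 56 × g | 30.856 g | 32.256 g |
| Ratio at 28 days | 1.304 | 1.244 |
| Expected, 33 days: 66 × g | 36.366 g | 38.016 g |
| Ratio at 33 days | 1.107 | 1.055 |

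By volume, (50 − 5 × 0.67)/37.52 = 46.65/37.52 = 1.243 at either strength. The gap at 5% comes from the approximate inputs: 0.551/0.67 = 0.822 g/mL, so 50 mL would weigh 41.1 g, not 43 g. With 41.1 g, (41.1 − 2.755)/30.856 = 1.243. At 15%, 0.576/0.67 = 0.860 g/mL gives 43.0 g, so weight and volume agree.

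**Unreturned pumps in the section 9.3 formula.** A full container weighs about 78 to 84 g gross (protocol section 5). After priming (2.755 g or 2.88 g) that is about 75 to 81 g. If the pump is not returned, nothing is subtracted and the whole weight counts as drug.

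Take a subject who used exactly the instructed amount from all 12 pumps and failed to return one:

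- 5%: expected 12 × 30.856 = 370.3 g; computed 11 × 30.856 + 75.2 to 81.2 = 414.7 to 420.7 g, or 112% to 114%.
- 15%: expected 12 × 32.256 = 387.1 g; computed 11 × 32.256 + 75.1 to 81.1 = 429.9 to 435.9 g, or 111% to 113%.

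One lost pump therefore looks like 48 weeks of 11 to 14% over-use.

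**The case against.** Several stronger readings are tempting, and the documents do not support them.

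- **That over-application is invisible in every summary.** SAP section 5.2 tabulates major violations by arm, and dosing non-compliance is one category. It is not limited to under-use, so it could count some over-users. It states no threshold, direction, amount or data source. The shell for Table 14.3.5 (exposure and compliance) is in a separate document that was not supplied. The supported statement is that the SAP text describes no by-arm weight summary.
- **That compliance rests on recall alone.** Protocol sections 7.2.3 and 7.2.4 have sites ask subjects about missed doses, but sites also weigh the returned pump. The Dosing CRF page is not shown, and nothing says whether the weight informs the entry.
- **That 5% subjects have a firm 30% headroom.** That figure applies the 43 g fill to a gel whose own stroke weight and volume imply about 41 g.
- **That the ceiling can be turned into a likely extra daily dose.** Reaching it means emptying nearly every pump, and some surplus is needed to cover the visit window. Weight measures gel removed from the pump, not gel applied.

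The consequence is also bounded. No endpoint or analysis population uses the compliance percentage, all analyses are descriptive, and delivered drug stays available by subject in a listing. The protocol does not promise a weight-based summary. These points limit the finding. They do not remove the cap or repair the unreturned-pump rule.

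**Conclusion.** The concern holds in this form. The section 7 percentage is bounded at 100% by its definition and cannot show over-application or partial strokes. The SAP text describes no by-arm summary of the measured dose, and the section 9.3 formula overstates delivery for any subject with an unreturned pump.

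The possible over-use that would go unshown is about 24% per 28-day pump at either strength by volume, or 24 to 30% by weight for the 5% gel. It falls to about 6% (15%) to 11% (5%) by weight at 33 days. These are upper limits under daily dosing and assume all gel can be dispensed. The gram and volume constants come from the supplied Amendment 01, while the SAP follows Amendment 4, so they may have changed. The cap itself does not depend on them. The change should be made, but the point does not invalidate any planned safety table.

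**What to change.** In SAP sections 7 and 9.3 and Table 14.3.5:

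1. For each returned pump, compute (primed weight − returned weight) / grams per actuation for that strength, taken from the current protocol amendment. Divide by the doses expected over the same pump interval.
2. Summarise the subject-level ratio by arm: n, mean, SD, median, minimum and maximum, with the number and percentage of subjects below 80% and above 110%. State that these cut-offs are descriptive choices. An upper cut-off of 120% would be barely reachable, because the ceiling under daily dosing is near 124%.
3. Report the number of unreturned pumps and exclude them from total drug delivered.
4. Show divided-dosing periods separately. SAP Table 1 allows them, but the supplied documents do not say how half a dose is dispensed or whether the rest is discarded.
5. Footnote that spilled or discarded gel counts as used.
6. Keep the missed-dose percentage alongside.

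The cost is SAP wording and some programming. The weights are already collected, so no visits or subject burden are added. The drawback is that lost gel inflates the ratio, which is why both measures should be shown.
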